7.11.3 Outliers

As a general rule, all values, including outliers will be analyzed.

7.11.4 Visits Windows

The study protocol gives the overall study schedule and the permissible intervals for visits expressed as the number of days relative to the first study medication date (Day 1).

For all study assessments reported by visit, the value which assessment day is the latest collected within the corresponding analysis visit window will be used. If more than one value is collected that day, then the latest value will be used in the analysis.

Analysis Visit windows, as depicted in [Table 31](#) below, will be used for the following study assessments reported by visit:

- Central laboratory parameters (except Lipid Panel),
- Vital Signs,
- ECG parameters,
- Exposure.

Table 31 Analysis Visit Windows

CRF Visit	Target Day ^a	Analysis Visit Windows Actual Assessment Day	Analysis Visit
Screening		Day -42 to Day -1	Screening
Day 1	Day 1	Day 1	Baseline
Week 1	Day 7 * (Week #) + 1	Day 2 to Day 11	Week 1
Week 2	Day 7 * (Week #) + 1	Day 12 to Day 21	Week 2
Week 4 – 22	Day 7 * (Week #) + 1	[Target Day – 7, Target Day +6]	Week 4 - 22
Week 24	Day 7 * (Week #) + 1	[Target Day – 7, Target Day + 13]	Week 24
Week 28 – 100	Day 7 * (Week #) + 1	[Target Day – 14, Target Day + 13]	Week 28 - 100
Week 104/EOT (for completers)	Day 7 * (Week #) + 1	[Target Day – 14, Target Day + 28]	Week 104
EOT Visit (for premature discontinuations) or unscheduled (on-treatment)	NA	NA	Analysis Visit corresponding to the actual visit window
EOT + 2 Weeks Visit	14 Days after EOT visit day	NA	EOT + 2 weeks
EOS Visit	28 Days after EOT visit day	NA	EOS
Unscheduled	NA	Day of EOT+1, Day of EOT+20	EOT+2 weeks
Unscheduled	NA	Day of EOT+21, Day of EOT+31	EOS

^a: Relative to Day 1 (first dose date of study medication)

Analysis Visit windows, as depicted in [Table 32](#) below, will be used for the quality of life efficacy study assessments:

Table 32 Analysis Visit Windows for QoL

CRF Visit	Target Day ^a	Analysis Visit Windows Actual Assessment Day	Analysis Visit
Day 1	Day 1	Day 1	Baseline
Week 8	Day 7 * (Week #) + 1	[Target Day – 14, Target Day + 13]	Week 8
Week 12	Day 7 * (Week #) + 1	[Target Day – 14, Target Day + 27]	Week 12
Week 28	Day 7 * (Week #) + 1	[Target Day – 28, Target Day + 27]	Week 28
Week 36	Day 7 * (Week #) + 1	[Target Day – 28, Target Day +27]	Week 36
Week 52	Day 7 * (Week #) + 1	[Target Day – 56, Target Day + 83]	Week 52
Week 76	Day 7 * (Week #) + 1	[Target Day – 84, Target Day + 97]	Week 76
Week 104/EOT (for completers)	Day 7 * (Week #) + 1	[Target Day – 98, Target Day + 28]	Week 104
EOT Visit (for premature discontinuations)	NA	NA	Analysis Visit corresponding to the actual visit window
Unscheduled	NA	NA	Analysis Visit corresponding to the actual visit window

^a: Relative to Day 1 (first dose date of study medication)

Analysis Visit windows, as depicted in [Table 33](#) below, will be used for the Lipid Panel, including LDL cholesterol efficacy study assessment:

Table 33 Analysis Visit Windows for Lipid Panel

CRF Visit	Target Day ^a	Analysis Visit Windows Actual Assessment Day	Analysis Visit
Day 1	Day 1	Day 1	Baseline
Week 4	Day 7 * (Week #) + 1	Day 2 to Day 42	Week 4
Week 8	Day 7 * (Week #) + 1	[Target Day – 14, Target Day + 13]	Week 8
Week 12	Day 7 * (Week #) + 1	[Target Day – 14, Target Day + 27]	Week 12
Week 20	Day 7 * (Week #) + 1	[Target Day – 28, Target Day + 27]	Week 20
Week 28	Day 7 * (Week #) + 1	[Target Day – 28, Target Day + 27]	Week 28
Week 36	Day 7 * (Week #) + 1	[Target Day – 28, Target Day + 27]	Week 36
Week 44	Day 7 * (Week #) + 1	[Target Day – 28, Target Day + 27]	Week 44
Week 52	Day 7 * (Week #) + 1	[Target Day – 28, Target Day + 55]	Week 52
Week 68	Day 7 * (Week #) + 1	[Target Day – 56, Target Day + 55]	Week 68
Week 84	Day 7 * (Week #) + 1	[Target Day – 56, Target Day + 69]	Week 84
Week 104/EOT (for completers)	Day 7 * (Week #) + 1	[Target Day – 70, Target Day + 28]	Week 104

Table continued on next page

CRF Visit	Target Day ^a	Analysis Visit Windows Actual Assessment Day	Analysis Visit
EOT Visit (for premature discontinuations)	NA	NA	Analysis Visit corresponding to the actual visit window
EOS Visit	NA	Last assessment between Day 2 and study termination day	EOS
Unscheduled	NA	NA	Analysis Visit corresponding to the actual visit window

^a: Relative to Day 1 (first dose date of study medication)

For the MMRM analyses, which requires one value per visit, one analysis Hb value for each planned visit will be used.

For the ANCOVA analyses, which use the average, all available values in the analysis windows will be used for the calculation.

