
Pharmacodynamics
	
Pharmacodynamic data may be submitted to population pharmacodynamic (PPD) or population pharmacokinetic/pharmacodynamic (PPK/PD) modeling. When deemed necessary, data from this study may be combined with data from other studies. Results will be reported in a separate PPK/PD modeling report.

V. FLOW CHART AND SCHEDULE OF ASSESSMENTS

Figure 1 Flow Chart

[figure not shown]

Table 1 Schedule of Assessments

Study Period:	Screening			Treatment ^a				Follow-up			Unscheduled Visits	Post study Follow-up Every 6 months until projected wk 108
	Up to 6 Weeks			Day 1 ^b	Weekly (wks 1 to 2) ± 2 days	Every 2 Weeks (wks 4 to 24) ± 2 days	Every 4 Weeks (wks 28 to 100) ± 3 days	EOT (wk 104) ± 3 days	EOT + 2 wks ± 3 days	EOS (EOT + 4 wks) ± 3 days		
Visit / Week:	S1	S2	S3									
Written informed consent	X											
Randomization				X								
Eligibility criteria	X			X								
Demographics and medical history including tobacco use	X											
Weight	X			X		wks 12, 24	wks 36, 52, 76	X		X	O ^c	
Physical examination	X			X		wks 12 ^d , 24 ^d	wks 36 ^d , 52 ^d , 76 ^d	X		X ^c	O ^{c, d}	
Blood pressure ^e , heart rate ^e , respiratory rate ^g	X	X	X	X	X	X	X	X		X	O ^c	
CBC with WBC differential, red cell indices and platelet count	X			X	X	wks 4, 8, 12, 20	wk 28 and every following 8 wks	X		X	O ^c	
Reticulocyte count, Hemoglobin content of reticulocytes (CHR)	X			X	X	wks 4, 6, 8, 12, 16, 20	wk 28 and every following 8 wks	X		X	O ^c	
Hemoglobin ^h		X	X			X	X		X		O ^c	
HemoCue® assessment ⁱ				X	X	X	X				O ^c	
Serum chemistry (incl LFT)	X			X		wks 4, 8, 12, 20	wk 28 and every following 8 wks	X	X	X	O ^c	
LFTs ^j					wk 2	wks 6, 16					O ^c	
Serum Lipid panel (fasting whenever possible)	X			X		wks 4, 8, 12, 20	wks 28, 36, 44, 52, 68, 84	X		X	O ^c	
Serum iron, ferritin, TIBC, TSAT	X			X		wks 4, 8, 12, 20	wk 28 and every following 8 wks	X		X	O ^c	
HbA1c	X			X		wk 12	wks 28, 36, 44, 60, 84	X		X	O ^c	
Vitamin B ₁₂ , folate	X											
HIV Immunoassay, HBsAg, anti-HCV antibody	X											

Table continued on next page

Study Period: Visit / Week:	Screening			Treatment ^a				Follow-up			Unscheduled Visits	Post study Follow-up
	Up to 6 Weeks	Day 1 ^b	Weekly (wks 1 to 2) ± 2 days	Every 2 Weeks (wks 4 to 24) ± 2 days	Every 4 Weeks (wks 28 to 100) ± 3 days	EOT (wk 104) ± 3 days	EOT + 2 wks ± 3 days	EOS (EOT + 4 wks) ± 3 days	Every 6 months until projected wk 108			
S1	S2									S3		

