For subjects with use of ESA, the time to first use of ESA is calculated as:

$$(\text{First event date} - \text{Analysis date of first dose intake} + 1) / 365.25$$

With 'First event date' defined as 'Date of first ESA' and 'Analysis date of first dose intake' defined in Section [6.5.4](#)

For a subject without use of ESA, the time to censoring is calculated as:

$$(\text{Date of End of Efficacy Emergent Period} - \text{Analysis date of first dose intake} + 1) / 365.25$$

With date of End of Efficacy Emergent Period defined in Section [7.11.6](#)

6.1.3.11 Change from BL to each post-dosing study visit in Total cholesterol, LDL/High-density Lipoprotein (HDL) ratio, Non-HDL cholesterol, Apolipoproteins A1 and B, ApoB/ApoA1 ratio

For each sample the following will be calculated:

- LDL/HDL ratio (LDL Cholesterol divided by HDL Cholesterol)
- Non-HDL cholesterol (Total Cholesterol minus HDL Cholesterol)

Change from baseline to each post-dosing study visit will be calculated for the following lipid parameters:

- Total cholesterol
- LDL cholesterol
- HDL cholesterol
- Low-density lipoprotein (LDL) / high-density lipoprotein (HDL) ratio
- Non-HDL cholesterol
- Triglyceride
- Apolipoproteins A1 and B (ApoA1 and ApoB)
- ApoB/ApoA1 ratio.

All available data will be summarized descriptively for all parameters above, regardless of fasting status.

No imputation will be performed in case of a missing value. If several values are available in the same window, one value will be used, as defined in [Table 33](#) and Section [7.11.4](#)

Baseline assessment is the assessment from Day 1 visit. If this value is missing, then the latest screening period value will be used as baseline.

6.1.3.12 Occurrence of mean LDL cholesterol <100 mg/dL calculated over weeks 12 to 28

The evaluation period is defined as the average of all available LDL cholesterol values in weeks 12-28 (visit at 12, 20 and 28 weeks, as defined in [Table 33](#) and Section [7.11.4](#)). The occurrence of mean LDL cholesterol <100 mg/dL over weeks 12 to 28 will then be defined as a binary variable (Yes/No), where "Yes" is defined as mean LDL cholesterol <100 mg/dL over weeks 12 to 28.

No imputation will be performed in case of a missing value.

This endpoint will be reported on fasting values and regardless of fasting status.

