Furthermore, the total amount of IV Iron used during the efficacy emergent period as well as for Day 1 to week 36, weeks 37 to 52 and weeks 53 to 104.

Time to first use of IV iron will also be analyzed similarly as in Section 7.4.2.7

Superiority will be declared if the upper bound of the two-sided 95% confidence interval of the hazard ratio of the two treatment arms is below 1.

7.4.3.10 Occurrence and time to first use of ESA. Number of ESA-Week per year

The number and percentage of subjects with ESA use as rescue therapy, and the number of ESA-weeks/year will be reported descriptively by treatment arm.

Time to first use of ESA will also be analyzed similarly as in Section 7.4.2.7 (except that all data during the Efficacy Emergent Period will be taken into account for the analysis).

The analysis will be done on the FAS.

Superiority will be declared if the upper bound of the two-sided 95% confidence interval of the hazard ratio of the two treatment arms is below 1.

7.4.3.11 Change from BL to each post-dosing study visit in Total cholesterol, LDL/High-density Lipoprotein (HDL) ratio, Non-HDL cholesterol, Apolipoproteins A1 and B, ApoB/ApoA1 ratio

Descriptive statistics (value, change from baseline) by visit and treatment arm. Descriptive statistics will also be reported regardless of fasting status.

7.4.3.12 Occurrence of mean LDL cholesterol <100 mg/dL calculated over weeks 12 to 28

The number and percentage of subjects with mean LDL cholesterol less than 100 mg/dL (fasting values and regardless fasting status) on average in weeks 12-28 will be reported by treatment arm and by baseline value.

7.4.3.13 Occurrence of achieved antihypertensive treatment goal in CKD subjects (SBP < 130 mmHg and DBP < 80 mmHg) based on the mean SBP and mean DBP calculated over weeks 12 to 28.

The number and percentage of subjects with achieved antihypertensive treatment goal over an evaluation period defined as the average of available values in weeks 12-28 will be reported by treatment arm.

7.4.3.14 Health related Quality of Life Questionnaires Change from BL to the average value of weeks 12 to 28

The following questionnaires will be analyzed:

- SF-36 (Physical Component Score (PCS));
- FACT-An (Anemia Subscale (“Additional Concerns”), Total FACT-An Score);
- EQ-5D 5L (VAS Score);
- Work Productivity and Activity Impairment Questionnaire: Anemic Symptoms (WPAI:ANS).

SF-36 and FACT-An

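### SAP Table 33 labels each subject's last post-baseline lipid value as EOS, so on-treatment values enter the descriptive lipid row that should hold only off-drug samples

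*SAP*

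**What the plan says.** SAP 7.11.4 sets the visit windows. Table 31 covers the central laboratory parameters other than lipids. Its EOS visit has the target "28 Days after EOT visit day", and unscheduled samples map to EOS only within "Day of EOT+21, Day of EOT+31".

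Table 33 "will be used for the Lipid Panel, including LDL cholesterol efficacy study assessment". Its EOS row has no target day, and its window is "Last assessment between Day 2 and study termination day". The general rule in the same section is that "the value which assessment day is the latest collected within the corresponding analysis visit window will be used".

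SAP 6.1.3.11 sends the by-visit lipid parameters to Table 33 and states: "No imputation will be performed in case of a missing value. If several values are available in the same window, one value will be used". SAP 7.11.1 adds that endpoints without inferential analysis are not imputed. SAP 7.4.3.11 makes the by-visit lipid analysis descriptive: "Descriptive statistics (value, change from baseline) by visit and treatment arm".

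The Schedule of Assessments takes lipids at screening, Day 1, Weeks 4, 8, 12, 20, 28, 36, 44, 52, 68 and 84, EOT and EOS. There is no lipid sample at EOT + 2 weeks. Panels at unscheduled visits are optional.

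**The concern.** A row headed EOS should describe subjects about four weeks after treatment ended. Under Table 33 it describes each subject's last lipid value, whenever that was drawn after Day 1. For a subject whose only post-baseline panel was at Week 4, the Week 4 value would be printed as EOS.

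EOS is the only scheduled lipid sample taken off drug. On-drug values in that row pull its mean towards the on-treatment mean, so an effect that had gone by EOS would appear partly to persist. Nothing in a table titled by visit would warn the reader that some entries were carried from earlier visits.

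**Working it through.** The plan states no figure for this rule, so there is none to reproduce. The check converts the windows to study days, compares the two tables, and then works out what the mixing does.

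**1. Windows in days.** Target day = 7 × week + 1. Table 33 then gives:

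| Visit | Days |
|---|---|
| Week 4 | 2–42 |
| Week 8 | 43–70 |
| Week 12 | 71–112 |
| Week 20 | 113–168 |
| Week 28 | 169–224 |
| Week 36 | 225–280 |
| Week 44 | 281–336 |
| Week 52 | 337–420 |
| Week 68 | 421–532 |
| Week 84 | 533–658 |
| Week 104 | 659–757 |

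The week windows run without a gap from Day 2 to Day 757. The EOS window starts on Day 2 and contains all of them.

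**2. Width of the EOS window.** Take study termination at the latest day the visit tolerance allows, EOT + 28 + 3 = EOT + 31.
- 104-week completer: EOT is Day 729. The window is Days 2–760, or 759 days. Days 2–729 are 728 of these, and 728/759 = 96% fall on or before EOT.
- 52-week completer: EOT is Day 365. The window is Days 2–396, or 395 days. Days 2–365 are 364 of these, and 364/395 = 92%.
- Table 31 window for unscheduled samples, 104-week completer: Days 750–760, or 11 days.

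These shares describe the window. They are not the chance that a given EOS value is on-treatment, because a real EOS sample is the last value and is normally the one selected.

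**3. Whose values are affected.** Only subjects with at least one post-Day-1 lipid value and no EOS sample. Unless they had an unscheduled panel after EOT, their entry was drawn at or before the EOT visit.

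**4. Effect on the row mean.** Let p be the fraction of subjects in the row with no EOS sample, D_on the mean on-drug change and D_off the true off-drug change. Assume the subjects without an EOS sample have the average on-drug change. Then

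reported EOS change = (1 − p) × D_off + p × D_on.

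- If D_off = 0, the row shows p × D_on. For an assumed p of 5% to 40%, that is 5% to 40% of the on-drug change.
- If D_off = 0.5 × D_on, the row shows (0.5 + 0.5p) × D_on. Over the same range that is 52.5% to 70% of the on-drug change, instead of 50%.

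The documents give neither p nor D_on; the range for p is assumed.

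**5. Reach.** The key secondary LDL endpoint averages the Week 12, 20 and 28 windows (SAP 6.1.2.2), and so does the endpoint of mean LDL below 100 mg/dL (6.1.3.12). EOS enters neither. It enters the by-visit descriptive summaries in 7.4.3.11, and other by-visit descriptive lipid output built on Table 33.

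**The case against.** **The row may be meant only for EOS-visit records.** Its CRF Visit column reads EOS Visit, and Table 31's EOS row works from that label with no day window. A programmer could read Table 33 the same way. But the window text does not say so, and the Day 2 lower bound would then have no purpose. Even if that was the intent, the row needs rewording, because two programmers could produce different tables.

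**Selecting an observed value is not imputation.** SAP 6.1.3.11 itself sends value selection to Table 33. That is fair as a matter of terms. In effect, though, a visit without a sample is filled from an earlier one, which is last observation carried forward.

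**The number affected may be small.** This stands. Protocol 3.3 asks subjects who discontinue treatment to complete EOT, EOT + 2 weeks and EOS, so stopping drug early does not by itself mean a missing EOS sample.

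Four stronger inferences are tempting, and the documents do not support them:
- *That the LDL claim is compromised because LDL is a key secondary endpoint.* EOS is not part of that endpoint.
- *That the plan relies on EOS lipids to show reversal after withdrawal.* No objective or listed endpoint concerns this. EOS is simply the only scheduled off-drug lipid sample, and optional unscheduled panels could add others.
- *That the distortion differs by arm.* SAP Appendix 7 raises possibly different rates between arms as a sign of informative censoring in time-to-event analyses. It says nothing about missing EOS lipid samples.
- *That a value appearing in both a week row and the EOS row is an error of double counting.* By-visit rows are not pooled, so this biases no estimate.

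**Conclusion.** The EOS row of Table 33 is wrong as written. It is a last-value rule labelled EOS, it departs from Table 31 without a stated reason, and it conflicts with the no-imputation statements in 6.1.3.11 and 7.11.1. It should be corrected, but the consequence is limited to descriptive by-visit lipid summaries. The confirmatory LDL test, the fixed sequence and type I error do not depend on it.

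The direction of the distortion follows from the rule: the EOS mean moves towards the on-treatment mean. The simple result, p times the on-drug change, rests on complete reversal by EOS and on subjects without an EOS sample having the average on-drug change. The documents establish neither. They also supply no p and no on-drug change, so no figure in mg/dL can be given.

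**What to change.** In Table 33, replace the EOS row with the Table 31 rule:
- the EOS visit sample, about 28 days after EOT, is EOS;
- unscheduled samples from EOT+21 to EOT+31 map to EOS, with a matching exception in Table 33's Unscheduled row;
- otherwise EOS is missing.

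If a last-value summary is wanted, give it a separate row labelled *Last post-baseline value*.

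While the table is open, state that an EOS sample cannot fill Week 104. The Week 104 window ends on Day 757, which is also the nominal EOS day for a 104-week completer (729 + 28), and the latest value in a window is the one used.

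The cost is a small table edit, the matching program change, and slightly fewer subjects in the EOS lipid rows.

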7.11.5 End of Safety Emergent Period

The end of Safety Emergent Period will be defined as :

- **Minimum [Analysis date of Last Dose + 28 days , max(EOS Visit, Date of death)]** in case Analysis date of Last Dose = Date of Last Dose
- **Minimum [(Analysis date of Last Dose + 28 days , max(EOS Visit, Date of death))]** in case Analysis date of Last Dose = Date of the End of Extended Treatment Visit (due to missing date of Last Dose) and the subject is treatment completer or discontinued due to any reason apart from Lost to follow up.
- **Analysis date of Last dose** in case Analysis date of Last Dose = Date of the End of Extended Treatment Visit (due to missing date of Last Dose) and the subject discontinued due to Lost to follow up.
- **Analysis date of Last dose** in case Analysis date of Last Dose = Date of last available assessment (due to missing date of last dose and date of the End of Extended Treatment Visit). In case a subject died, then **Minimum [Date of last available assessment + 28 days , Date of death]**.

With Analysis Date of Last Dose defined in Section 6.5.4

7.11.6 End of Efficacy Emergent Period

For all subjects, the end of Efficacy Emergent Period will be defined as :

- **Minimum (Analysis date of Last Dose + 7 days , EOT Visit)**

8 DOCUMENT REVISION HISTORY

Version	Date	Changes	Comment/rationale for change
1.0	28-May-2014	NA	Document finalized
2.0	21-January-2016	
 1) Reduction of the number of sensitivity analyses for the secondary endpoints. 2) New ordering for the key secondary endpoints. 3) Implementation of the Time to event approach for the PPS and adjustment of the relevant sections. 4) Change from ITT to All Randomized as per Astellas standard. Definition remains unchanged. 5) Use of the Safety Emergent Period (i.e last dose + 28 days) as evaluation period by default for the safety endpoints. 6) Use of the Efficacy Emergent Period (i.e last dose + 7 days) as evaluation period by default for most of the efficacy time to event endpoints. 7) Use of “Time to censoring” instead of “time at risk” for patient with no event for more clarity. 8) Clarification of time to censoring for events evaluated during the Safety Emergent Period/Efficacy Emergent 	
 1) Due to harmonization with Fibrogen 060 study SAP and to limit the additional analyses . 2) Due to the importance of the QoL endpoints and the harmonization with Fibrogen 060 study SAP. 3) PPS definition has been revised in order to limit the exclusion of data by using a time to event approach rather than creating one PPS set for each period of interest. 4) Astellas standards requirement. 5) Decision agreed by the study team to use a consistent approach for all the safety endpoints by extending the evaluated period up to 28 days after last dose, which matched the AE analyses. 6) Decision agreed with the study team to use a consistent approach for time to event efficacy endpoints by extending the evaluated period up to 7 days after last dose. 7) Clarification of the wording. Time to censoring is more appropriate. 8) Based on the new definitions of Efficacy/Safety Emergent period, time to censoring for all time to

Version	Date	Changes	Comment/rationale for change
		
Period.
 
9) Time to PCS vital signs added.
 
10) Time to PCS ECG focused to QTc instead of all ECG assessments.
 
11) Additional censoring rules for the post-dialysis data (used for some time to event related to AEs).
 
12) Update regarding derivation of MAP values : average of the 3 measurements instead of 2 (now in line with FG SAP).
 
13) Implementation of primary efficacy endpoint for FDA (change in Hb from baseline to the average level between week 28 and week 52) and description of statistical analyses including sensitivity analyses for missing data
 
14) Implementation of time to first hospitalization, time to first occurrence of serum creatinine doubled, time to first potential EH (2 different criteria separately), time to dialysis.
 
15) Reduction in the number of analyses of subgroup of interests.
	
events have been updated accordingly.
 
9) Time to PCS were already planned for lab and ECG but not for Vital signs. Decision was taken to provide them as well.
 
10) Time to event for PCS ECG other than QTcF was considered not of interest.
 
11) In order to assess the impact of dialysis on incidence rates of AEs, sensitivity analyses will be conducted by censoring patients at the date of dialysis.
 
12) Using the average of all 3 measurements is more efficient and is consistent with Fibrogen 060 study SAP.
 
13) This additional endpoint has been added in protocol amendment 1.0. Sensitivity analyses for missing data were added following FDA feedback on Fibrogen 060 study. Both Fibrogen and Astellas now in line regarding this endpoint.
 
14) Due to harmonization with Fibrogen 060 study SAP and the expected difference in treatment durations
 
15) Due to harmonization with Fibrogen 060 study SAP.

Version	Date	Changes	Comment/rationale for change
		
16) Addition of the analysis of percentage of time when Hb > 12, 13 or 14.
 
17) MMRM model added for number of RBC and volume of RBC during the treatment period.
 
18) Removal of descriptive analysis on the categorical change form baseline in Total FACT-An Score.
 
19) Removal of the descriptive analysis on change from day of first dialysis to week 4 and week 12 of dialysis for SF-36, FACT-AN scores, EQ-5D, WPAI.
 
20) Updated rule for complete missing start date and end date for concomitant medications. In that case, the medication will be considered as both previous and concomitant instead of only concomitant. For the analysis of monthly IV Iron use, MMRM has been replaced by ANCOVA.
 
21) Additional tables run on group of subjects enrolled after protocol amendment implementation
	
16) Due to harmonization with Fibrogen 060 study SAP.
 
17) The concept of percentage of time with high Hb values was implemented in order to account for differences in individual treatment durations.
 
18) Inferential analysis for RBC was missing in the v1.0.
 
19) Descriptive statistics for categorical change not necessary since analysis on absolute change already planned and considered sufficient.
 
20) Exploratory summary statistics of SF-36, FACT-AN scores, EQ-5D, WPAI for patients on dialysis not required since this is a small subset of patients and not based on the randomized population.
 
21) Previous rule considered too conservative since a missing year of start is usually for previous medications than concomitant. Decision was taken to consider such medications as both previous and concomitant.
 
22) MMRM model for monthly IV Iron was not adapted due the data distribution. Since monthly average will be

Version	Date	Changes	Comment/rationale for change
			
calculated, ANCOVA is more appropriate.
 
23) Added in order to assess the impact of protocol amendment 1.0.

3.0	06-November-2017	
 1) Removal of the reporting for date informed consent for genotyping and genotyping sample. 2) Number and percentage of subjects with drug related TEAEs leading to death added. 3) Use of SBP \geq170 mmHg AND an increase from BL \geq 20 mmHg or as DBP \geq 110 mmHg, AND an increase from BL \geq 15 mmHg for the definition of hypertension. 4) Use of the Safety Emergent Period as evaluation period to be considered a concomitant medication. 5) ATC codes for Iron-chelating agents were updated. 6) Belarus was added in the list of countries for Region B. 7) Use of the Efficacy Emergent Period as evaluation period to be considered for the definition of rescue therapy. 8) Removal of the criterion "at least one Hb value $>$13 g/dL during the Efficacy Emergent Period" for the definition of Potential Excessive Hematopoiesis (EH). 	
 1) Decision agreed by the study team. 2) Astellas standards requirement 3) Due to harmonization with Fibrogen 060 study SAP. 4) Decision agreed by the study team. 5) The ATC codes in previous version were not correct as they actually did not cover the Iron supplementation agents 6) Protocol requirement. 7) Decision agreed with the study team to use a consistent approach for rescue therapy by extending the evaluated period up to 7 days after last dose. 8) Due to harmonization with Fibrogen 060 study SAP.

Version	Date	Changes	Comment/rationale for change
		9) For the analysis of number of RBC packs and volume, MMRM has been replaced by ANCOVA	9) MMRM model for RBC packs and volume was not adapted due the data distribution. Since monthly average will be calculated, ANCOVA is more appropriate.
		10) Removal of the calculation of the amount of IV iron in monthly intervals during the Efficacy Emergent Period.	10) Decision agreed by the study team not to report Mean IV Iron for each month but only for the period of interest.
		11) Removal of the supplementary analysis for each post-dosing timepoint for subjects with mean LDL cholesterol less than 100 mg/dL. Average W12-W28 should be done for both regardless and fasting.	11) Decision agreed by the study team.
		12) Implementation of the derivation of the hospitalization duration. When hospitalization is ongoing, the date of end of the Efficacy Emergent Period will be used.	12) Decision agreed by the study team to be more accurate.
		13) Removal of other baseline factors including: Diabetes mellitus, age, gender, BMI, baseline eGFR, baseline CRP, ferritin, TSAT, CHr, Hypertension from ANCOVA with MI.	13) Due to harmonization with Fibrogen 060 study SAP.
		14) Update the calculation of the number of days of hospitalization per PEY as: Minimum ((Date of discharge, End of Efficacy Emergent Period) – Date of admission + 1) / [(Duration of Efficacy Emergent Period).	14) Decision agreed by the study team to be consistent with the definition.
		15) No comparison for IV Iron between treatment arms.	15) Due to the very small number of subjects with IV Iron.

Version	Date	Changes	Comment/rationale for change
		
16) Figure added with the comparison between central laboratory hemoglobin (g/dL) and HemoCue hemoglobin (g/dL).
 
17) Removal of the analysis for subjects who have reached Hb \geq 11.0 g/dL prior to week 28.
 
18) For time to first occurrence of serum creatinine doubled compared with baseline, a subject will be counted with an event either for doubled serum creatinine or ESRD, whichever comes first. Otherwise, we censor at date of last non-missing serum creatinine assessment during the Safety Emergent Period.
 
19) For WPAI scale, the number and proportion of employed subjects was summarized by visit and treatment arm.
 
20) Fatigue subscale score added for FACT-An questionnaire.
 
21) Time to All Deaths including Post study FU added.
 
22) Time to AEs by eGFR categories (<15 vs ≥ 15 mL/min/1.73m²) added.
 
23) Number of events and event rate (per 100 patient years) during the Safety Emergent Period with TEAEs added.
 
24) New sensitivity analysis (MMRM) for change to the
	
16) Decision agreed by the study team to check the differences between the two methods.
 
17) Decision agreed by the study team
 
18) Decision agreed by the study team to be consistent with the definition for time to first occurrence of serum creatinine doubled compared with baseline.
 
19) Decision agreed by the study team to check the number of employed subjects by visit and treatment arm.
 
20) Descriptive statistics fatigue were added due to a request from Health Economics and Outputs Research Department.
 
21) Decision agreed by the study team.
 
22) Decision agreed by the study team.
 
23) Decision agreed by the study team to compare treatments in a fair way due to potential difference in exposure between the two arms.
 
24) Decision agreed by the study team.

Version	Date	Changes	Comment/rationale for change
		
average Hb in weeks 28-52 including all Hb values up to end of treatment visit.
 
25) Interaction term baseline*visit added to the main MMRM model for Hb analysis
	
25) Based on internal statistical guidance and check on model fit.

4.0	08-March-2018	
1) Two additional subgroup analyses [Baseline CRP category (\leqULN vs. $>$ ULN)] and Baseline Iron Repletion Status category [(TSAT \geq 20% and ferritin \geq 100 ng/mL) vs. others] added for the primary efficacy endpoints and the key secondary efficacy endpoint in Hb (week 28 – week 36)
	
1) Baseline CRP group (CRP \leqULN vs. CRP $>$ ULN) is considered as a marker for inflammation which may affect treatment response. A subgroup analysis is added to explore the consistency of the effect of roxadustat on the Hb related primary efficacy parameters. Iron repletion status may affect treatment response and is added for consistency with Fibrogen 060 study SAP.

5.0	11-Jul-2018	
1) Time to Rescue Therapy during the first 24 weeks was replaced by Time to Rescue Therapy during the treatment period as Key Secondary Efficacy endpoint. Endpoint at 24 weeks was therefore considered as Other Secondary endpoint
 
2) VT and PF SF-36 scores have been switched in the hierarchical order of the key secondary endpoints
 
3) eGFR slope over time was added at the bottom of the list of key secondary endpoint
 
4) Details were added in All Randomized section regarding exclusion of subjects from site 70051
 
5) Additional analyses on adverse
	
1) Due to harmonization with Fibrogen 060 study SAP.
 
2) Due to harmonization with Fibrogen 060 study SAP.
 
3) Due to harmonization with Fibrogen 060 study SAP.
 
4) Site 70051 was terminated due to GCP violations and it is now clearly mentioned in the population section that those subjects are excluded from all analysis set.
 
5) Due to harmonization

Version	Date	Changes	Comment/rationale for change
		
event were added considering events occurring up to last dose +_7 days (i.e OT-7)
 
6) Details regarding derivation of CV history were added in relevant section
 
7) Time to first dialysis was changed to Time to chronic dialysis or renal transplant
	
with Fibrogen 060 study SAP.
 
6) To provide additional details about derivation.
 
7) Due to harmonization with Fibrogen 060 study SAP.

5.0	18-Jul-2018	
Time to event endpoints: For the following endpoints (new or existing), IPCW analysis is added. Additional endpoints of interest are added as indicated by new.
 
a. Rescue therapy: Time to first use of rescue therapy [composite of RBC transfusions, IV iron supplementation and rescue ESA] Time to first use of RBC transfusion Time to first use of IV iron supplementation Time to first use of ESA
 
b. Hospitalization: Time to first hospitalization
 
c. CKD progression: Time to CKD progression (composite of doubling serum creatinine, chronic dialysis or renal transplant, and Death) (new) Time to doubling serum creatinine (new) Time to chronic dialysis or renal transplant Time to chronic dialysis or renal transplant or occurrence for a subject who died (new) Time to at least 40% decrease in eGFR from baseline, chronic dialysis or renal transplant (new) Time to at least 40% decrease in eGFR from baseline (new)
 
d. Adverse Events: Time to serious TEAE Time to death Time to TEAE with grade 3 or higher Time to TEAE by SOC (>10% for a SOC in total SAF)
	
Due to harmonization with Fibrogen 060 study SAP.

5.0	18-Jul-2018	
Appendix 8 is added about inverse probability censoring weighted model
	
To provide details about inverse probability censoring weighted

Version	Date	Changes	Comment/rationale for change
			model
5.0	18-Jul-2018	Rate of progression of CKD measured by annualized eGFR slope over time: Analysis is updated to use non-log transformed eGFR values.	To perform log transformed analysis only if residual analysis indicates heteroscedasticity
5.0	18-Jul-2018	A summary is added for onset of common ($\geq 5\%$ in Any Treatment Group) TEAEs by Treatment Duration: < 3 months, ≥ 3 to ≤ 6 months, > 6 to ≤ 12 months, > 12 months	To provide summary of common TEAEs by treatment duration.
5.0	02-Aug-2018	End point time to doubling of serum creatinine or ESRD is updated as Time to doubling of serum creatinine or chronic dialysis or renal transplant	To be consistent with Time to CKD progression Endpoint.

